## HISTORY FORM

Version	Date	Reason for change
V1.0	10 July 2019	Initial version
V2.0	25 January 2021	
Trial design: addition of more precise description of the design
 
Demographic criteria: addition of Geographic region definition and precision of the Medical History and Concomitant Disease coding
 
Secondary Efficacy criteria: clarification in the formulae of LBR
 
General considerations: addition of a statement regarding ICH E9 (R1) handling, precision of ITT principle for efficacy analysis and derivation for time to event
 
Handling of missing data: precision of the rules for imputing missing dates
 
Examination of subgroup: addition of subgroup analysis by main demographic parameters and magnetic field
 
Disposition of patients: precision of the analyzed set used and further description of analyses
 
Disposition of patients: handling of potential premature withdrawal due to COVID pandemic
 
Deviations: update of definition wording and status and addition of deviations
 
Deviations: handling of potential deviation due to COVID pandemic
 
Datasets analyzed: Addition of 3 datasets for efficacy analysis and precision of the presentation
 
Demographics: in procedure for study diagnosis, addition of 3 classes (mammogram, Ultrasound, PET-CT) and indication of the selection by scanning the specify text when other is ticked
 
Efficacy: secondary analysis of the primary criteria: addition of magnetic field in subgroup analysis and modification of the subgroup analysis by organ.
 
Efficacy: secondary analysis of the primary criteria updates for intra and inter analyses, clarification that analyses are performed using FAS1 and FAS2
 
Efficacy: secondary analysis of the primary criteria: addition of global analysis with all readers in the same model and addition of analysis with non-matching lesions
 
Efficacy: secondary analysis of the primary criteria: Lesion-level analysis with size of lesion added as co-factor.
 
Efficacy: secondary criterion: patient's treatment plan: addition of analysis taken into account the nature (non malignant/malignant/not assessable) of the diagnosis done at unenhanced MRI
 
Efficacy: secondary criterion: patient's treatment plan: addition of the therapeutic management based on unenhanced MRI
 
Efficacy: secondary analysis of the primary criteria: Readers of different body regions put together in a way to have more balanced meta-readers in terms of concordance reads
 
Exposure: addition of two periods for description, from inform consent signed to 1st IMP injection and from inform consent signed to end of trial
 
Safety: Clinical laboratory evaluation: precision of unit for laboratory parameters
 
Safety: Clinical laboratory evaluation: description of derivation of urea parameter from blood urea nitrogen
 
Safety: Clinical laboratory evaluation: correction of classification of eGFR, creatinine, BUN at baseline for shift tables

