#### *Qualitative analysis*

Shift tables presenting relative change from baseline in classes *versus* baseline in classes will be displayed for *serum creatinine*, *eGFR*, *BUN* and *cystatin C*.

Baseline data will be classified as follows (no baseline categories will be used for cystatin C):

SI units	Conventional units

 
• Serum creatinine (umol/L): 
 
○ < 60
 
○ <math>\geq</math> 60 and < 100
 
○ <math>\geq</math> 100
 
 
 
	
 
• Serum creatinine (mg/dL): 
 
• < 0.66
 
• <math>\geq</math> 0.66 and < 1.1
 
• <math>\geq</math> 1.1
 
 
 

 
• eGFR (mL/min/1.73m^2): 
 
○ < 60
 
○ <math>\geq</math> 60 and < 90
 
○ <math>\geq</math> 90
 
 
 
	
 
• eGFR (mL/min/1.73m^2): 
 
• < 60
 
• <math>\geq</math> 60 and < 90
 
• <math>\geq</math> 90
 
 
 

 
• BUN (mmol/L): 
 
○ < 2
 
○ <math>\geq</math> 2 and < 4
 
○ <math>\geq</math> 4 and < 6
 
○ <math>\geq</math> 6
 
 
 
	
 
• BUN (mg/dL): 
 
• < 5.6
 
• <math>\geq</math> 5.6 and < 11.2
 
• <math>\geq</math> 11.2 and < 16.8
 
• <math>\geq</math> 16.8
 
 
 

 
• Cystatin C (U/L): 
 
○ All
 
 
 
	
 
• Cystatin C (U/L): 
 
• All
 
 
 

Relative change from baseline will be calculated as follows:  $100^* \text{ (post injection measurement - baseline measurement) / baseline measurement}$ . Relative change from baseline will be classified as follows:

- $\leq -50\%$ .
- $> -50\%$  and  $\leq -25\%$ .
- $> -25\%$  and  $\leq -15\%$ .
- $> -15\%$  and  $< 0\%$ .
- $\geq 0\%$  and  $< 15\%$ .
- $\geq 15\%$  and  $< 25\%$ .
- $\geq 25\%$  and  $< 50\%$ .
- $\geq 50\%$ .

Numbers and percentages of patients in each class will be presented in both SI and conventional units.

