#### 6.1.3.4 *Laboratory data*

Table 14.3.3.11 Hematology Data - Raw data and Change from Baseline – SI Units – Safety Set

CONFIDENTIAL	STATISTICAL ANALYSIS PLAN PHASE III TRIAL GDX-44-011 VERSION NO. 2.0      DATED 25 JANUARY 2021	████████ Page 53 / 57
--------------	---	--------------------------

Table 14.3.3.2 Hematology Data - Raw data and Change from Baseline – Conventional US Units – Safety Set

Table 14.3.3.3 Biochemistry Data - Raw data and Change from Baseline – SI Units – Safety Set

Table 14.3.3.4 Biochemistry Data - Raw data and Change from Baseline – Conventional US Units – Safety Set

Table 14.3.3.5 Hematology Data - Raw data and Change from Baseline by Body Region – SI Units – Safety Set

Table 14.3.3.6 Hematology Data - Raw data and Change from Baseline by Body Region – Conventional US Units – Safety Set

Table 14.3.3.7 Biochemistry Data - Raw data and Change from Baseline by Body Region – SI Units – Safety Set

Table 14.3.3.8 Biochemistry Data - Raw data and Change from Baseline by Body Region – Conventional US Units – Safety Set

Table 14.3.3.9 Shift Table of Serum Creatinine, eGFR, BUN and Cystatin C between Baseline Measurement and Post-Injection Measurement – SI units – Safety Set

Table 14.3.3.10 Shift Table of Serum Creatinine, eGFR, BUN and Cystatin C between Baseline Measurement and Post-Injection Measurement – Conventional US units – Safety Set

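### The mg/dL cut-offs for baseline creatinine classes in SAP 5.7.3 are not the equivalents of the umol/L cut-offs, so patients in two narrow bands fall in different rows of the two shift tables

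*SAP*

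**What the plan says.** SAP 5.7.3, under Qualitative analysis, plans shift tables of relative change from baseline, in classes, against baseline, in classes. It covers serum creatinine, eGFR, BUN and cystatin C. The baseline classes are introduced with "Baseline data will be classified as follows (no baseline categories will be used for cystatin C") and set out in an SI column and a conventional column:

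| Parameter | SI cut-offs | Conventional cut-offs |
|---|---|---|
| Creatinine | 60, 100 umol/L | 0.66, 1.1 mg/dL |
| eGFR | 60, 90 mL/min/1.73m² | 60, 90 mL/min/1.73m² |
| BUN | 2, 4, 6 mmol/L | 5.6, 11.2, 16.8 mg/dL |

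The section ends: "Numbers and percentages of patients in each class will be presented in both SI and conventional units". SAP 6.1.3.4 accordingly lists two outputs on the Safety Set: Table 14.3.3.9 in SI units, and Table 14.3.3.10, "Shift Table of Serum Creatinine, eGFR, BUN and Cystatin C between Baseline Measurement and Post-Injection Measurement – Conventional US units – Safety Set". The SAP's version history for V2.0 records a "correction of classification of eGFR, creatinine, BUN at baseline for shift tables".

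**The concern.** The two tables show the same patients and the same measurements, so they should differ only in the unit label. The eGFR cut-offs are identical in the two columns and the BUN cut-offs are a straight conversion. Nothing in the SAP says that the creatinine classes are approximate or meant to differ. If the creatinine pairs are not equivalent, some patients sit in one baseline row of the SI table and another row of the conventional table, and a reader comparing the two finds unexplained discrepancies.

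Conversion cannot be avoided. Protocol 8.5 has creatinine measured locally, and Protocol 11.3.8 requires results in both unit systems, with original units only listed.

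**Working it through.** **Inputs.** The cut-offs are those in SAP 5.7.3. Neither document gives a creatinine conversion factor, although SAP 5.7.3 does give one for urea from BUN. The factor is therefore an assumption, taken from creatinine's molar mass (C4H7N3O, 113.12 g/mol):

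- mg/dL = umol/L × 113.12 / 10,000, so 1 mg/dL = 10,000 / 113.12 = 88.4 umol/L.

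**The plan's own figures.** 0.66 / 60 = 0.011 and 1.1 / 100 = 0.011. Both printed cut-offs follow from one factor of 0.011 mg/dL per umol/L, that is 1 / 0.011 = 90.9 umol/L per mg/dL. The computed factor is 113.12 / 10,000 = 0.0113, so 0.011 looks like that value cut to two significant figures.

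**Correct equivalents.**

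- 60 / 88.4 = 0.679 mg/dL and 100 / 88.4 = 1.131 mg/dL, that is 0.68 and 1.13.
- In reverse, 0.66 × 88.4 = 58.3 umol/L and 1.1 × 88.4 = 97.2 umol/L.
- Varying the factor from 88.0 to 88.42 gives 0.679-0.682 and 1.131-1.136, never 0.66 or 1.1.

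**Check on the neighbouring row.** BUN converts at 28.014 / 10 = 2.8014: 2, 4 and 6 mmol/L become 5.60, 11.21 and 16.81 mg/dL. These match the printed 5.6, 11.2 and 16.8, so creatinine is the only row that fails.

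**Who moves.**

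| Baseline (umol/L) | Class in Table 14.3.3.9 (SI) | Class in Table 14.3.3.10 (conventional) |
|---|---|---|
| 58.3 to <60 | lowest | middle |
| 97.2 to <100 | middle | highest |
| all others | same | same |

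Among whole-number umol/L values, 59, 98 and 99 switch if the conversion is left unrounded. If mg/dL is rounded to two decimals, 58 (0.656, rounds to 0.66) and 97 (1.097, rounds to 1.10) switch as well.

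**How many.** The documents give no creatinine distribution, so this is illustration only, with a normal baseline and 300 patients.

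| Assumed mean, SD (umol/L) | Continuous values | Whole umol/L, unrounded mg/dL | Whole umol/L, mg/dL to two decimals |
|---|---|---|---|
| 70, 15 | 4.6% | 2.9% | 5.4% |
| 75, 18 | 5.1% | 3.4% | 5.9% |
| 80, 20 | 5.5% | 3.8% | 6.2% |

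The range is about 3-6%: 0.029 × 300 ≈ 9 to 0.062 × 300 ≈ 19 patients. On continuous values the upper band alone holds 1.2%, 2.6% and 3.6% in the three cases, about 4 to 11 of 300. A lognormal baseline with mean 65-85 and SD 15-25 umol/L gives 4.3-5.4% on continuous values, about 13-16 of 300.

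**What does not move.** SAP 5.7.3 defines relative change as 100 × (post − baseline) / baseline. The unit cancels, so a patient's relative-change class is the same in both tables, apart from any rounding of converted values. Only the baseline row can differ.

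**The case against.** The strongest case on the other side is that this is a rounding slip in a descriptive table and changes no conclusion. Most of that stands:

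- Only two narrow bands are affected. Everyone else is classed identically.
- Summed over baseline rows, the number of patients with, say, a rise of 50% or more is the same in both tables.
- Renal eligibility in Protocol 4.2 uses eGFR, and the eGFR shift classes are identical in the two columns. The post-contrast kidney injury definition in Protocol 7.2.11 uses change in creatinine, not these classes.
- The size depends on an assumed distribution and on reporting precision, neither of which is in the documents.

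A reader might go further and infer that submissions in different units would report different renal shift counts overall, or that the error matters because renal risk is read from the top creatinine class. The documents support neither. Overall shift counts agree because relative change is unit-free, and no rule in the protocol or SAP attaches a decision to a baseline of 100 umol/L or more.

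A reader might also quote a larger share by supposing that sites report mg/dL to one decimal, so that everyone recorded at 1.1 mg/dL changes row. The documents state no such practice. That figure would in any case replace the estimate above, not add to it.

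The objection does not remove the mismatch itself. The V2.0 correction of these classes does not repair it either, because the mismatch is in the current text.

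**Conclusion.** Wrong as written, minor. Followed literally, SAP 5.7.3 puts patients with a baseline of 58.3 to <60 or 97.2 to <100 umol/L one class higher in Table 14.3.3.10 than in Table 14.3.3.9. Baseline-row counts and within-row percentages will then disagree between two tables of the same data. The effect stops there.

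The mismatch rests only on the conversion factor, and it holds at every factor tried from 88.0 to 88.42. The estimate of roughly 3-6% of patients is softer. It rests on an assumed mean of 70-80 and SD of 15-20 umol/L, and on how values are recorded and rounded.

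**What to change.** In SAP 5.7.3, state that the baseline creatinine class is assigned once, from the SI value, and carried into both shift tables. Print the conventional cut-offs as 0.68 and 1.13 mg/dL.

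Reprinting the cut-offs alone removes nearly all of the discrepancy but not quite all: a baseline of exactly 60 umol/L converts to 0.679 mg/dL and, left unrounded, would still fall below 0.68. Single assignment leaves no residual mismatch.

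The cost is two numbers and a sentence in the SAP, recorded in a new version or a documented note, plus a small programming change. Table 14.3.3.10 would need a rerun only if it has already been produced.

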
#### *Individual clinically significant abnormalities*

For each hematology and chemistry parameter, number and percentage of patients with at least one clinically significant value (according to the investigator) during the trial will be presented by contrast agent groups.

#### **5.7.4. Vital signs, physical findings and other observations related to safety**

Raw values and changes from baseline of Systolic/Diastolic Blood Pressure (mmHg) and Pulse Rate (beats/min) will be summarized by period, timepoints and contrast agent groups.

Descriptive statistics of raw data and change from baseline for each vital signs' parameter will be computed at each time point. The baseline value will be the last vital signs measured prior to the injection of the 1st contrast agent.

Injection-site tolerance will be summarized qualitatively by timepoints and contrast agent groups. Pain evaluation will be quantitatively summarized by timepoints and contrast agent groups for patient reporting pain.

CONFIDENTIAL	STATISTICAL ANALYSIS PLAN PHASE III TRIAL GDX-44-011 VERSION NO. 2.0      DATED 25 JANUARY 2021	[REDACTED] Page 44 / 57
--------------	---	----------------------------

Listings of injection-site tolerance and vital signs will be provided in CSR appendix 16.2.9.

#### **5.7.5. Concomitant medications/procedures**

The number and percent of patients taking concomitant medications and concomitant procedures will be presented by contrast agent groups and overall. According to the information available in the clinical database, a medication/procedure can be concomitant to the two periods (if any) and so counted in both contrast media groups. In this case, it will count only once in the total column

Summary table (number and % of patients) grouped by the first and the last level of ATC code will be presented for concomitant medications and will be sorted by descending frequency of the first ATC code (anatomical class) and, within each first ATC, by descending frequency of the last level of ATC code (chemical class) according to the column Total. The chemical class code will be presented along with the name in the table.

Summary table (number and % of patients) grouped by SOC and PT will be presented for concomitant procedures and will be sorted by descending frequency of SOC) and, within each SOC, by descending frequency of the PT according to the column Total.

Listing will be presented in CSR appendix 16.2.4.

CONFIDENTIAL	STATISTICAL ANALYSIS PLAN PHASE III TRIAL GDX-44-011 VERSION NO. 2.0	████████ Page 45 / 57
--------------	--	--------------------------

## 6. LIST OF TABLES, FIGURES AND LISTINGS

### 6.1. Contents of clinical study report section 14

This section lists all Tables and Figures in the order in which they are expected to appear in Section 14 of the CSR.

#### 6.1.1. Demographic data

##### 6.1.1.1 Disposition

- Table 14.1.1.1 Patient Overall Disposition – Screened patients Set
- Table 14.1.1.2 Patient Overall Disposition by Body Region – Screened patients Set
- Table 14.1.1.3 Reasons for Screening Failure – Screened patients Set
- Table 14.1.1.4 Reasons for Premature Discontinuation – Screened patients Set – Randomized Patients
- Table 14.1.1.5 Reasons for Premature Discontinuation by body region – Screened patients Set – Randomized Patients
- Table 14.1.1.6 Number of Patients by Center – Screened patients Set
- Table 14.1.1.7 Patient Disposition by Visit– Screened patients Set

##### 6.1.1.2 Protocol Deviations

- Table 14.1.2.1 Major Protocol Deviations – Screened patients Set
- Table 14.1.2.2 Non Major Protocol Deviations – Screened patients Set

##### 6.1.1.3 Data Sets Analysed

- Table 14.1.3.1 Analysis Data Sets: Full Analysis and Per Protocol Sets– Screened patients Set
- Table 14.1.3.2 Analysis Data Sets: Safety Set – Screened patients Set

##### 6.1.1.4 Demographics and Baseline Characteristics

- Table 14.1.4.1 Demographic Data – FAS 1
- Table 14.1.4.2 Demographic Data by Body Region – FAS 1
- Table 14.1.4.3 Demographic Data – FAS 2
- Table 14.1.4.4 Demographic Data by Body Region – FAS2
- Table 14.1.4.5 Demographic Data – Safety Set
- Table 14.1.4.6 Trial Disease Diagnosis According to Primary SOC and PT - FAS 1
- Table 14.1.4.7 Imaging Procedure Documenting the Trial Disease - FAS 1
- Table 14.1.4.8 Trial Disease Diagnosis According to Primary SOC and PT - FAS 2
- Table 14.1.4.9 Imaging Procedure Documenting the Trial Disease - FAS 2
- Table 14.1.4.10 Medical History According to Primary SOC and PT - FAS 1
- Table 14.1.4.11 Concomitant Disease According to Primary SOC and PT - FAS 1
- Table 14.1.4.12 Medical History by Body Region According to Primary SOC and PT - FAS 1
- Table 14.1.4.13 Concomitant Disease by Body Region According to Primary SOC and PT - FAS 1
- Table 14.1.4.14 Medical History According to Primary SOC and PT - FAS 2
- Table 14.1.4.15 Concomitant Disease - According to Primary SOC and PT - FAS 2
- Table 14.1.4.16 Medical History by Body Region According to Primary SOC and PT - FAS 2
- Table 14.1.4.17 Concomitant Disease by Body Region - According to Primary SOC and PT - FAS 2
- Table 14.1.4.18 Medical History - According to Primary SOC and PT - Safety Set
- Table 14.1.4.19 Concomitant Disease According to Primary SOC and PT - Safety Set
- Table 14.1.4.20 eGFR at Visit 2 and Visit 4 - Safety Set
- Table 14.1.4.21 Prior Medications According to ATC first and fourth levels - FAS 1
- Table 14.1.4.22 Prior Medications According to ATC first and fourth levels - FAS 2

CONFIDENTIAL	STATISTICAL ANALYSIS PLAN PHASE III TRIAL GDX-44-011 VERSION NO. 2.0      DATED 25 JANUARY 2021	████████████████
--------------	---	------------------

Table 14.1.4.23 Patient's Contrast Agent Intolerance History - Safety Set

*6.1.1.5 MRI Examination*

Table 14.1.5.1 MRI Examination - FAS 1  
Table 14.1.5.2 MRI Examination - FAS 2

*6.1.1.6 Compliance with Trial product*

Table 14.1.6.1 Compliance with Trial Product – FAS 1  
Table 14.1.6.2 Compliance with Trial Product – FAS 2

**6.1.2. Efficacy data**

*6.1.2.1 Primary Efficacy Co-primary Criteria*

Primary Analysis of the Co-primary Criteria

Table 14.2.1.1 Co-primary criteria 1 - Off-Site Readings – Mixed Model – FAS 1  
Table 14.2.1.2 Co-primary criteria 2 - Off-Site Readings – Mixed Model – PPS 2

Supportive Analyses of the Co-primary criteria

Table 14.2.1.3 Co-primary criteria 1 - Off-Site Readings – Mixed Model – PPS 1  
Table 14.2.1.4 Co-primary criteria 2 - Off-Site Readings – Mixed Model – FAS 2

**Descriptive Statistics**

Table 14.2.1.5 Co-primary criteria 1- Off-Site Readings - Descriptive Statistics - FAS 1  
Table 14.2.1.6 Co-primary criteria 2- Off-Site Readings - Descriptive Statistics - PPS 2  
Table 14.2.1.7 Co-primary criteria 1- Off-Site Readings - Descriptive Statistics - PPS 1  
Table 14.2.1.8 Co-primary criteria 2- Off-Site Readings - Descriptive Statistics – FAS 2

**Assay sensitivity**

Table 14.2.1.9 Lesion visualization criteria - Off-Site Readings – MRI with Gadobutrol– PAIRED vs PRE - Mixed Model - FAS 2

**Subgroup analysis**

*Body region*

Table 14.2.1.10 Lesion visualization criteria - Off-Site Readings – MRI with Gadopiclenol– PAIRED vs PRE - Mixed Model adjusted by body region – FAS1  
Figure 14.2.1.11 Lesion visualization criteria - Off-Site Readings – MRI with Gadopiclenol– PAIRED vs PRE - Forest Plot by body region – FAS1  
Table 14.2.1.11 Lesion visualization criteria - Off-Site Readings – MRI with Gadopiclenol vs MRI with Gadobutrol - Mixed Model adjusted by body region – FAS2  
Figure 14.2.1.12 Lesion visualization criteria - Off-Site Readings – MRI with Gadopiclenol vs MRI with Gadobutrol - Forest Plot by body region – FAS2  
Table 14.2.1.12 Lesion visualization criteria - Off-Site Readings - MRI with Gadopiclenol– PAIRED vs PRE - Descriptive Statistics by body region – FAS1  
Table 14.2.1.13 Lesion visualization criteria - Off-Site Readings - MRI with Gadopiclenol vs MRI with Gadobutrol - Descriptive Statistics by body region – FAS2

*Organ*

Table 14.2.1.14 Lesion visualization criteria - Off-Site Readings – MRI with Gadopiclenol– PAIRED vs PRE - Mixed Model adjusted by organ – FAS1  
Figure 14.2.1.13 Lesion visualization criteria - Off-Site Readings – MRI with Gadopiclenol– PAIRED vs PRE - Forest Plot by organ – FAS1

Table 14.2.1.15	Lesion visualization criteria - Off-Site Readings – MRI with Gadopiclenol vs MRI with Gadobutrol - Mixed Model adjusted by organ – FAS2
Figure 14.2.1.4	Lesion visualization criteria - Off-Site Readings – MRI with Gadopiclenol vs MRI with Gadobutrol - Forest Plot by organ – FAS2
Table 14.2.1.16	Lesion visualization criteria - Off-Site Readings - MRI with Gadopiclenol– PAIRED vs PRE - Descriptive Statistics by organ – FAS1
Table 14.2.1.17	Lesion visualization criteria - Off-Site Readings - MRI with Gadopiclenol vs MRI with Gadobutrol - Descriptive Statistics by organ – FAS2
Demographics	parameters and magnetic field
Table 14.2.1.18	Lesion visualization criteria - Off-Site Readings – MRI with Gadopiclenol– PAIRED vs PRE - Mixed Model adjusted by demographic parameters and magnetic field – FAS1
Figure 14.2.1.5	Lesion visualization criteria - Off-Site Readings – MRI with Gadopiclenol– PAIRED vs PRE - Forest Plot by demographic parameters and magnetic field – FAS1
Table 14.2.1.19	Lesion visualization criteria - Off-Site Readings – MRI with Gadopiclenol vs MRI with Gadobutrol - Mixed Model adjusted by demographic parameters and magnetic field – FAS2
Figure 14.2.1.6	Lesion visualization criteria - Off-Site Readings – MRI with Gadopiclenol vs MRI with Gadobutrol - Forest Plot by demographic parameters and magnetic field – FAS2
Table 14.2.1.20	Lesion visualization criteria - Off-Site Readings - MRI with Gadopiclenol– PAIRED vs PRE - Descriptive Statistics by demographic parameters and magnetic field – FAS1
Table 14.2.1.21	Lesion visualization criteria - Off-Site Readings - MRI with Gadopiclenol vs MRI with Gadobutrol - Descriptive Statistics by demographic parameters and magnetic field – FAS2

### Additional Analyses of the Primary Criterion

## Intra- Off-Site Reader Variability

Table 14.2.1.22	Lesion visualization criteria - Intra-Off-Site Reader Variability - FAS 1
Figure 14.2.1.7	Lesion visualization criteria - Intra-Off-Site Reader Variability – Border delineation - Bland-Altman Graphs - FAS 1
Figure 14.2.1.8	Lesion visualization criteria - Intra-Off-Site Reader Variability – Internal morphology - Bland-Altman Graphs - FAS 1
Figure 14.2.1.9	Lesion visualization criteria - Intra-Off-Site Reader Variability – Degree of contrast enhancement - Bland-Altman Graphs - FAS 1
Table 14.2.1.23	Lesion visualization criteria - Intra-Off-Site Reader Variability - FAS 2
Figure 14.2.1.10	Lesion visualization criteria - Intra-Off-Site Reader Variability – Border delineation - Bland-Altman Graphs - FAS 2
Figure 14.2.1.11	Lesion visualization criteria - Intra-Off-Site Reader Variability – Internal morphology - Bland-Altman Graphs - FAS 2
Figure 14.2.1.12	Lesion visualization criteria - Intra-Off-Site Reader Variability – Degree of contrast enhancement - Bland-Altman Graphs - FAS 2

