## 2.2. Efficacy criteria

### 2.2.1. Primary criteria

#### **Primary criteria 1: Lesion visualization criteria for gadopiclenol-enhanced MRI compared to unenhanced MRI (off-site read):**

The lesion visualization assessment is based on 3 co-primary criteria: border delineation, internal morphology and degree of contrast enhancement assessed on the images acquired during the MRI performed with gadopiclenol.

Each Independent Blinded Reader (IBR) will record each of the 3 co-primary criteria for up to 3 most representative lesions, on Paired images (contrast-enhanced + unenhanced images) versus Pre contrast images (unenhanced images) on a 4-point scale as described below:

- **Border delineation:**

Delineation of the lesion border is defined as the distinction of lesion from surrounding tissues, structures, or edema; and the detection of extent of the lesion. This criterion will be assessed through the following scale:

- 1 = None: no or unclear delineation
- 2 = Moderate: some areas of clear delineation but also with some significant areas of non-distinct delineation
- 3 = Good: almost clear but not complete delineation
- 4 = Excellent: border outline is sharp with clear and complete delineation

- **Internal morphology:**

Internal morphology of the lesion includes an identification of lesion architecture and the intra-lesion features such as necrosis, hemorrhage and vascularity. This criterion will be assessed through the following scale:

- 1 = Poor: poorly seen
- 2 = Moderate: majority of lesion is poorly seen but with minor parts of lesion visible
- 3 = Good: majority of lesion is clearly seen but with minor parts of lesion invisible
- 4 = Excellent: lesion is well seen and can see “through” lesion to observe any complex areas of necrosis or hemorrhage or cyst formation

- **Degree of contrast enhancement:**

This criterion will be a qualitative assessment (not based on signal intensity measurement) according to the following scale:

- 1 = No: no enhancement
- 2 = Moderate: weakly enhanced
- 3 = Good: clearly enhanced
- 4 = Excellent: clearly and brightly enhanced

The mean score for each of the 3 co-primary criteria of lesion visualization will be calculated as follows:

Mean score = (score of the lesion 1 + score of the lesion 2 (if any) + score of the lesion 3 (if any)) divided by the number of lesions (up to 3 most representative lesions).

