## Intra-reader variability

Intra-reader variability will be analyzed in a subgroup of 10% of patients randomly selected for whom the off-site readers have re-read the images.

Intra-reader variability will be presented using data from gadopiclenol period on FAS1 on the one hand and using paired images from gadopiclenol and gadobutrol on FAS2 on the other hand.

Intra-reader variability will be studied by a Bland-Altman graph:

- Average of 1st and 2nd reading on X axis.
- Difference 2nd reading - 1st reading on Y axis.
- Horizontal lines at Mean, Mean + 1.96SD and Mean - 1.96SD, where Mean and SD are the mean and the SD of the difference of 1st and 2nd readings

One scatter plot per reader will be presented.

CONFIDENTIAL	STATISTICAL ANALYSIS PLAN PHASE III TRIAL GDX-44-011 VERSION NO. 2.0      DATED 25 JANUARY 2021	████████ Page 32 / 57
--------------	---	--------------------------

Descriptive statistics and the Intra-Class Correlation (ICC) will also be provided. It will be based on a one-way random effect model without observed effect:

$$Y_{ijk} = \mu + \alpha_i + \varepsilon_{ijk}$$

with  $\alpha_i \sim N(0, \sigma_\alpha^2)$  and  $\varepsilon_{ijk} \sim N(0, \sigma_\varepsilon^2)$  and  $\varepsilon_{ijk}$  is independent of  $\alpha_i$ .

$$ICC = \sigma_\alpha^2 / (\sigma_\alpha^2 + \sigma_\varepsilon^2)$$

which is estimated by

$$(MS_\alpha - MS_\varepsilon) / (MS_\alpha + MS_\varepsilon)$$

where  $MS_\alpha$  and  $MS_\varepsilon$  are the mean sums of squares from the one-way ANalysis Of VAriance (ANOVA) model for between and within subjects, respectively.

SAS® procedure used for the analyses of this secondary efficacy criterion will be the following for each off-site reader:

```
ods output OverallANOVA =icc0;
proc glm data=intra;
  class subject MRI modality reading;
  model BV = subject MRI modality reading;
run;
data ICC;
  retain sb sw;
  set icc0 end=last;
  if source='Model' then sb=ms;
  if source='Error' then sw=ms;
  if last then do;
    ICC=round((sb-sw)/(sb+sw), 0.01);
    output;
  end;
run;
```

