#### Inter-reader variability

Inter-reader variability will be evaluated on the whole set of study patients, since each case was read by 3 different readers.

Inter-reader variability will be presented using data from gadopiclenol period on FAS1 on the one hand and using paired images from gadopiclenol and gadobutrol on FAS2 on the other hand.

The same methodology as the one presented above for intra-off-site variability will be applied. One scatter plot for each of the 3 comparisons will be presented. The factor “reader” will be used instead of the factor “reading” in the model.

Presentation of patients and lesions.

Number of patients and lesions by contrast agents and MRI modalities for all efficacy datasets will be displayed using All Randomized Set.

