## Inter-Off-Site Reader Variability

Table 14.2.1.24 Lesion visualization criteria - Inter-Off-Site Reader Variability - FAS 1  
 Figure 14.2.1.13 Lesion visualization criteria - Inter-Off-Site Reader Variability – Border delineation - Bland-Altman Graphs - FAS 1  
 Figure 14.2.1.14 Lesion visualization criteria - Inter-Off-Site Reader Variability – Internal morphology - Bland-Altman Graphs - FAS 1  
 Figure 14.2.1.15 Lesion visualization criteria - Inter-Off-Site Reader Variability – Degree of contrast enhancement - Bland-Altman Graphs - FAS 1  
 Table 14.2.1.25 Lesion visualization criteria - Inter-Off-Site Reader Variability - FAS 2

CONFIDENTIAL	STATISTICAL ANALYSIS PLAN PHASE III TRIAL GDX-44-011 VERSION NO. 2.0      DATED 25 JANUARY 2021	████████
--------------	---	----------

Figure 14.2.1.16 Lesion visualization criteria - Inter-Off-Site Reader Variability– Border delineation - Bland-Altman Graphs - FAS 2

Figure 14.2.1.17 Lesion visualization criteria - Inter-Off-Site Reader Variability - – Internal morphology Bland-Altman Graphs - FAS 2

Figure 14.2.1.18 Lesion visualization criteria - Inter-Off-Site Reader Variability - Degree of contrast enhancement - Bland-Altman Graphs - FAS 2

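### On its natural reading, the SAP pools unenhanced Pre reads with Paired reads in the FAS1 Bland-Altman graphs for degree of contrast enhancement, which could make the limits of agreement up to about 29% too narrow at a 1:1 mix

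*SAP*

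**What the plan says.** SAP section 5.6.2, Intra-reader variability, defines the data for the two analysis sets differently. For FAS1: "Intra-reader variability will be presented using data from gadopiclenol period on FAS1 on the one hand". For FAS2: "using paired images from gadopiclenol and gadobutrol on FAS2 on the other hand". The restriction to Paired images is attached to FAS2 only. The model code for the intra-class correlation in the same section has MRI modality as a factor, so Pre and Paired reads sit in one data set.

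The layout is then fixed: "One scatter plot per reader will be presented", with "Horizontal lines at Mean, Mean + 1.96SD and Mean - 1.96SD" of the differences between readings. The Inter-reader variability text uses the same FAS1 and FAS2 data, adopts the same method, and adds "One scatter plot for each of the 3 comparisons will be presented".

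SAP section 6.1.2.1 lists one FAS1 figure for this criterion for each type of variability: Figure 14.2.1.9, "Lesion visualization criteria - Intra-Off-Site Reader Variability – Degree of contrast enhancement - Bland-Altman Graphs - FAS 1", and Figure 14.2.1.15, "Lesion visualization criteria - Inter-Off-Site Reader Variability – Degree of contrast enhancement - Bland-Altman Graphs - FAS 1". Neither title mentions a split by image type.

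SAP section 2.2.1 has readers score Pre and Paired images on the same 4-point scale. For degree of contrast enhancement the lowest anchor is "1 = No: no enhancement". The score is a qualitative judgement by the reader.

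**The concern.** A Pre image contains no contrast agent. A reader asked how strongly a lesion enhances on it would be expected to choose the lowest score, at a first read and at a re-read, and so would a second reader. The difference is then near zero, however repeatable that reader is on enhanced images. Such points say almost nothing about repeatability for this criterion. In a shared plot they still enter the single SD and shrink the limits of agreement, and they pull the mean difference towards zero.

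The stake is how reader reliability is described for one of the three co-primary criteria. The FAS1 graphs could overstate repeatability and agreement, and show only about half of any systematic shift between readings or readers. They could also look better than the FAS2 graphs simply because the mix of images differs.

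**Working it through.** **Plan's own figure.** The documents give no expected limits, repeatability SD or correlation, so there is nothing to reproduce.

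**Inputs**
- *f*, the share of Pre differences. FAS1 patients must have both gadopiclenol Pre and Paired images (SAP section 5.2). Inter-reader variability uses the whole set of patients, so *f* is about 0.5 there. For the intra-reader graphs, Protocol section 8.4.8 says that 10% of cases are re-read, but not that both image sets of a case are. There, *f* = 0.5 is an assumption.
- *v*, the variance of Pre differences divided by that of Paired differences. It is 0 if every Pre read is scored 1. This is assumed and varied below.
- *m*, the mean Paired difference divided by its SD, *s*. The Pre mean difference is taken as 0.

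**Formula.** The pooled variance is the within-type plus the between-type part:

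SD(pooled) / SD(Paired) = √[(1 − f) + f·v + f(1 − f)·m²], and mean(pooled) = (1 − f) × mean(Paired).

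**Ideal case** (f = 0.5, v = 0, m = 0): √0.5 = 0.707, so the limits are 1 − 0.707 = 29.3% narrower. They become ±1.96 × 0.707s = ±1.39s in place of ±1.96s. With the n − 1 divisor and 30 re-read patients (10% of 300), the ratio is √(29/59) = 0.701, which is 29.9% narrower.

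**Departures from the ideal case** (assumed inputs, one changed at a time):

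| Change | Narrowing |
|---|---|
| f = 0.40 / 0.45 / 0.55 / 0.60 | 22.5% / 25.8% / 32.9% / 36.8% |
| v = 0.05 / 0.10 / 0.25 / 0.50 | 27.5% / 25.8% / 20.9% / 13.4% |
| m = 0.25 / 0.5 / 1 | 28.2% / 25.0% / 13.4% |

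The narrowing vanishes if v = 1 or if m reaches √2 = 1.41.

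**Example with a shift** (mean 0.4 and s = 0.7, both assumed; f = 0.5, v = 0). The pooled SD is 0.7 × √(0.5 + 0.25 × (0.4/0.7)²) = 0.534. Pooled limits are 0.2 ± 1.05, or −0.85 to 1.25. Paired-only limits are 0.4 ± 1.37, or −0.97 to 1.77. The pooled limits are 24% narrower and the mean is halved.

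**Example on the score scale.** If 40% of Paired re-reads differ by one point in either direction with no net shift (assumed), the Paired-only limits are ±1.96√0.4 = ±1.24. The pooled limits are ±1.96√0.2 = ±0.88.

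**Inter-reader shifts in the documents' own data.** The phase IIb table in Protocol section 11.2 gives contrast-enhancement means (SD) of 3.23 (0.80), 3.76 (0.58) and 3.68 (0.50). Independent reads are assumed, with f = 0.5 and v = 0:
- Readers 1 and 2: s = √(0.80² + 0.58²) = 0.988, m = 0.53/0.988 = 0.536, narrowing 24%.
- Readers 1 and 3: s = √(0.80² + 0.50²) = 0.943, m = 0.45/0.943 = 0.477, narrowing 25%.
- Readers 2 and 3: s = √(0.58² + 0.50²) = 0.766, m = 0.08/0.766 = 0.104, narrowing 29%.

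Positive correlation between readers would reduce *s*, raise *m* and lower these figures. That trial enrolled patients with brain lesions, so they are indicative only.

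**The case against.** A reader might infer that Pre images score 1 by definition, that half the differences are therefore forced to zero, and that the limits are 29% too narrow without condition. The documents do not support this. The anchor describes a score; no rule assigns that score to Pre images, and readers judge both image types. The 29% needs a 1:1 mix, zero Pre differences and no mean shift all at once, and the intra-reader mix is not stated. It is also tempting to say that the narrowed limits hold only 83% of Paired differences instead of 95%. That figure assumes normal differences. Scores are integers averaged over at most three lesions, so coverage moves in steps: in the 40% example, ±0.88 holds 60% and ±1.24 holds 100%. The 83% should not be relied on. All of this stands.

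Pooling is itself an inference. No sentence says that one SD is taken across image types, and the figure titles alone do not show it. The text of section 5.6.2 nevertheless points that way, and nothing elsewhere provides a split.

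Paired-only graphs are already planned for FAS2 (Figures 14.2.1.12 and 14.2.1.18), and a cluster of Pre points at score 1 and difference 0 would be visible on a FAS1 plot. Both help an alert reader. Neither changes where the FAS1 lines are drawn.

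Finally, no decision rests on these graphs. The SAP sets no acceptance limit for variability, and the two-of-three-readers rule (SAP section 3.8) uses each reader's own test. Reading this as a threat to the primary conclusions would be wrong. A floor effect is argued here for one criterion only, so a compulsory split of all three is not justified.

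**Conclusion.** The point holds in conditional form. As section 5.6.2 is written, the FAS1 intra- and inter-reader graphs pool Pre and Paired reads. For degree of contrast enhancement this would probably make the limits of agreement too narrow and would dilute any systematic difference.

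The narrowing is up to about 29% at a 1:1 mix, about 13% to 28% under modest Pre variability or a mean shift, and more than 29% if Pre reads exceed half the points. The mean difference is about halved at 1:1. These sizes rest on Pre scores sitting at or near 1, which is a reasonable expectation and can be checked in the data. They also rest on the 1:1 mix, which follows from the FAS1 definition for the inter-reader graphs and is assumed for the intra-reader graphs. The consequence is confined to supportive reader-variability output.

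**What to change.** In SAP section 5.6.2, Intra-reader and Inter-reader variability, state that for degree of contrast enhancement the FAS1 Bland-Altman mean and limits are computed separately for Pre and Paired images. Apply this to Figures 14.2.1.9 and 14.2.1.15, and split the matching descriptive statistics in Tables 14.2.1.22 and 14.2.1.24 in the same way. Give limits of agreement for Paired images only, and report Pre images as the percentage of reads scored 1. That percentage also tests the main assumption made here. State whether both image sets of a re-read case are re-read. A split for border delineation and internal morphology is optional.

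The cost is a few lines of SAP text and a by-modality run of output already planned, with no new data. The downside is a few more panels and probably wider limits for this criterion.
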